## 14. STATISTICS

### 14.1. Sample Size Determination

This is an open-label, single-arm safety and efficacy study. Subjects completing Study ADS-AMT-MS301 (up to approximately 540 subjects) will be eligible for enrollment.

### 14.2. Analysis Sets

The safety analysis set will include all subjects who receive at least one dose of study drug in study ADS-AMT-MS303 according to the treatment sequence (see [Section 14.5](#)) actually received.

The modified intent-to-treat (MITT) analysis set will include all subjects enrolled in the study who received at least one dose of study drug in study ADS-AMT-MS303 according to the randomized treatment sequence. It is understood that randomization here refers to the randomized assignment in study ADS-AMT-MS301.

The per-protocol (PP) analysis set will include all randomized and dosed subjects who provide Week 52 efficacy data and do not have any major protocol deviations that could confound this assessment.

### 14.3. Handling of Missing Data

This will be described in the statistical analysis plan.

### 14.4. Efficacy Endpoints

Endpoints will be derived using the Week 0 assessments as the baseline value. These endpoints will consist of the changes from Baseline/Week 0 at Weeks 12, 24, and 52 in the:

- T25FW (ft/sec) and also T25FW (sec)
- TUG (sec)
- 2MWT
- MSWS-12
- The proportion of Novel Responders at each study visit, where a Novel Responder is defined as a subject who has a  $\geq 20\%$  increase from Baseline/Week 0 to the study visit in walking speed measured using the T25FW. Subjects who fail to have an increase of at least 20% at the given study visit in the T25FW (ft/sec) (non-responders) or who discontinue the study prior to this visit will be included in the denominators.

## 14.5. Efficacy Analyses

All efficacy analyses will be based on the MITT, as well as the PP analyses set.

Endpoints will be summarized by treatment sequence depending on the treatment received in [Study ADS-AMT-MS301](#):

Sequence No.	Study ADS-AMT-MS301 Treatment	Study ADS-AMT-MS303 Treatment
1	Placebo	274 mg/d ADS-5102
2	137 mg/d ADS-5102	274 mg/d ADS-5102
3	274 mg/d ADS-5102	274 mg/d ADS-5102

Efficacy results will be analyzed by treatment sequences 1, 2, and 3 shown above and also by sequences 2 and 3 combined (ie, treatment sequence 1 versus 2 and 3 combined). Descriptive statistics (ie, mean, standard error, median, minimum/maximum, 95% confidence intervals [CI] for the changes from baseline) for each parameter at each study visit will be generated. Missing data will not be imputed. Graphical depictions of changes over time will be provided.

The proportion of Novel Responders in walking speed for each treatment sequence as well as pooled sequences 2 and 3 will also be characterized. The counts and percentages of Novel Responders, Non-Responders, and discontinuations at each study visit will be presented.

For parameters measured on a continuum (eg, MSWS-12, T25FW (ft/sec)), the treatment-sequence time trend will be explored using an MMRM model with the change from baseline as the dependent variable, fixed effects of treatment-sequence, study visit (ie week 12, 24 and 52), treatment-sequence by study visit interaction, baseline value as a covariate and an unstructured variance-covariance matrix for the within-subject residual variability. Appropriate contrasts comparing time trends between treatment-sequences will be derived from this model. For the proportion responders, a GEE (generalized estimating equation) model for a binomial variate will be used.

Details of all analyses will be provided in the statistical analysis plan (SAP) for this study.

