## 5. INTRODUCTION

This is an open-label extension (OLE) study for subjects who complete 16 weeks of study drug treatment and a Week 16 visit in Study ADS-AMT-MS301, “A 3-Arm, Multicenter, Double-Blind, Placebo-Controlled, Randomized Study to Assess the Efficacy and Safety of ADS-5102 Amantadine Extended Release Capsules in Multiple Sclerosis Patients with Walking Impairment.” The primary purpose of this study is to extend the evaluation of the safety and tolerability of ADS-5102, an extended-release (ER) capsule formulation of amantadine administered at 274 mg/d, in subjects with multiple sclerosis (MS) and walking impairment from 12 weeks, as in Study ADS-AMT-MS301, to 52 weeks or 64 weeks (including the duration of ADS-AMT-MS301). Additionally, this study is intended to provide supportive evidence of the efficacy of ADS-5102 as a treatment for walking impairment in MS (by way of treating the former ADS-AMT-MS301 placebo subjects), as well as an assessment of the durability of efficacy up to 64 weeks.

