## 7. INVESTIGATIONAL PLAN

### 7.1. Overall Study Design

This is a multicenter, open-label study of ADS-5102 (amantadine) extended release capsules in subjects with MS and walking impairment who completed study drug treatment for 16 weeks and completed a Week 16 visit in Study ADS-AMT-MS301.

Eligibility for inclusion in this study will require all subjects to be willing to abstain from prohibited medications.

All enrolled subjects will receive ADS-5102 at 137 mg for the first week, 205.5 mg for the second week, and 274 mg for the remainder of the 52-week open-label treatment period.

Subjects will return to the clinic for safety and efficacy assessments at Weeks 4, 12, 24, and 52. In addition, a telephone visit for safety assessments will be conducted at Week 2 and Week 38. Subjects who withdraw from the study prior to completion of the Week 52 visit will have an early termination (ET) visit that includes safety and efficacy assessments. Subjects who complete 52 weeks of open-label treatment will have a final visit for post-treatment safety follow-up and efficacy assessment at 54 weeks, 2 weeks after their Week 52 visit. The end of study (EOS) is defined as when a subject completes the safety follow-up or ET visit.

All study visits and efficacy assessments should be scheduled to occur at approximately the same time of day for each individual subject. Each subject's efficacy assessment should be performed by the same clinical rater, if possible.

Adverse events (AEs) and concomitant medications will be recorded beginning with the first dose of study drug and continuing through the last study visit.

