### 8.3. Subject Withdrawal Criteria

Subjects will be advised that they are free to withdraw from the study at any time. Reasons that subjects may be withdrawn from the study include the following:

- Subject discontinued study drug (see [Section 8.5](#)) and wishes to withdraw
- Subject consent is withdrawn
- Sponsor decision, after discussion with the investigator

If a subject is withdrawn from the study, all efforts will be made to complete the early termination visit that includes efficacy assessments and safety follow-up. In addition, women of childbearing potential will have a post-study pregnancy test performed at the early termination visit.

All information, including the reason for withdrawal, should be reported on the applicable pages of the case report form (CRF).

For subjects who are lost to follow-up, three documented attempts will be made to contact the subject for follow-up information, including reason for discontinuation and follow-up of AEs.

Subjects who withdraw from the study will not be replaced.

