## **8.5. Discontinuation of Study Drug**

Subjects should discontinue study drug if judged necessary by the investigator or sponsor, and reasons may include any of the following:

- eGFR falls below 60 mL/min/1.73 m^2, confirmed by repeat testing
- Need to take a medication that is excluded or that may interfere with study measurements
  - Subjects requiring MS treatment adjustment due to disease exacerbation or progression should be discussed with one of the Medical Monitors
- Intolerable or unacceptable AEs
- Positive pregnancy test

Subjects who discontinue study drug will be withdrawn from the study, and will have an early termination visit that includes efficacy assessments and safety follow-up (see [Section 12.8](#)).

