## 12.8. Early Termination Visit

- Assess and record concomitant medications
- Assess and record AEs
- Complete physical examination
- Obtain subject weight in kilograms
- Vital signs (blood pressure, respiratory rate, heart rate, and temperature)
- Blood sample for central laboratory analysis including hematology, serum chemistry, and eGFR
- Urinalysis
- Blood sample for serum pregnancy test in female subjects of childbearing potential
- MSWS-12, T25FW, TUG, and 2MWT assessments (Full details on how individual efficacy assessments are to be performed will be provided in the study manual. These assessments are to be done in this order.)
- C-SSRS
- Collect bottles and evaluate compliance
- Completion of Early Termination Visit CRF, including reason for early discontinuation. (If early termination is due to AE, then a brief narrative of the AE will be recorded in the allocated section of the Early Termination Visit CRF)

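### If dropout is related to response, the displayed Week 52 changes in the continuous walking measures overstate durability: they are observed-case, the MMRM is kept for between-sequence contrasts, and early termination tests have no assigned use

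*Combined protocol and SAP*

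**What the plan says.** Durability is a stated purpose of the study: the Introduction (Section 5) lists it "as well as an assessment of the durability of efficacy up to 64 weeks". The first secondary objective in Section 6.2 is T25FW speed at Week 52, followed by TUG, 2MWT and MSWS-12 at Week 52.

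- **Descriptive results.** Section 14.5 plans means, standard errors, 95% confidence intervals and graphs of change by visit and sequence, and adds "Missing data will not be imputed". Section 14.3 says of missing data only: "This will be described in the statistical analysis plan". No SAP text is in the material available here.
- **Model.** Section 14.5 plans an MMRM on change at Weeks 12, 24 and 52 to explore the sequence-by-time trend. Its contrasts compare time trends between sequences; the Synopsis says specific weeks between sequences.
- **Analysis sets.** Efficacy is analysed in the MITT and PP sets. Section 14.2 makes Week 52 efficacy data a condition for PP.
- **Responders.** Section 14.4 keeps subjects who discontinued before a visit in the Novel Responder denominator, and Section 14.5 tabulates discontinuations at each visit.
- **Leaving the study.** Section 8.5 says "Subjects who discontinue study drug will be withdrawn from the study". Section 8.3 lists, as a reason for withdrawal, a subject who stopped study drug "and wishes to withdraw".
- **Early termination (ET) tests.** Section 7.1 says that subjects who leave early "will have an early termination (ET) visit that includes safety and efficacy assessments", and Section 12.8 lists "MSWS-12, T25FW, TUG, and 2MWT assessments". The endpoints in Section 14.4 name only Weeks 12, 24 and 52. Table 3 shows ET in parentheses beside Week 52.

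**The concern.** All three sequences receive the same open-label target dose, so durability is a within-sequence question: how much of the change from baseline is still there at Week 52? For the continuous measures, the only results the protocol promises on that question are observed-case. If subjects whose walking responds poorly, or whose response fades, leave more often, the mean of those remaining can hold steady while the mean of all dosed subjects falls. Repeating the summary in the PP set is no check, because that set is also restricted to subjects seen at Week 52.

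The ET tests are the data best placed to show what happened to those who left, and the protocol does not say how they are used. Reading Table 3's label as permission to count an early exit as Week 52 would be a different error: a test taken after a few weeks would stand in for a year of treatment.

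**Working it through.** **There is no plan figure to reproduce.** The 540 in Section 14.1 is the number who could come from Study MS301. The protocol gives no effect size, SD or dropout rate for this study. Every dropout rate, difference and correlation below is an assumption.

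**1. Bias of an observed-case mean.** Let d be the fraction missing at Week 52, mC the mean change of those observed, and mD the mean change that the others would have shown.

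- Mean of all dosed subjects = (1 − d) × mC + d × mD
- Bias of the observed mean = mC − [(1 − d) × mC + d × mD] = d × (mC − mD)

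| d | mC − mD (ft/s) | Bias (ft/s) | Observed of 540 |
|---|---|---|---|
| 0.30 | 0.2 | 0.06 | 378 |
| 0.30 | 0.3 | 0.09 | 378 |
| 0.40 | 0.2 | 0.08 | 324 |
| 0.40 | 0.3 | 0.12 | 324 |
| any | 0 | 0 | 540 × (1 − d) |

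**2. What the planned model would do.** This was simulated in one group of 540 with 300 replicates. Assumed true mean changes were 0.30, 0.15 and 0.00 SD at Weeks 12, 24 and 52, so the effect is entirely lost. Correlations were 0.7 (Weeks 12-24), 0.6 (12-52) and 0.7 (24-52). Response-related dropout had a logit slope of 1 per SD. The likelihood estimate uses an unstructured covariance and no baseline covariate.

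| Dropout depends on | Retained at Week 52 | Observed-case mean (SD) | Likelihood estimate (SD) |
|---|---|---|---|
| Earlier observed change | 81% / 69% / 59% | +0.09 / +0.14 / +0.18 | 0.00 / 0.00 / 0.00 |
| The unseen value | 82% / 70% / 60% | +0.14 / +0.22 / +0.31 | +0.08 / +0.14 / +0.20 |

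The true value is 0.00 throughout. In the first mechanism, loss before Week 12 was random. The model removes the bias when dropout follows observed change and reduces it otherwise. That supports reporting the model and adding a sensitivity analysis.

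**3. Responder endpoint.** With discontinued subjects in the denominator, the reported rate is r × (1 − d). A 30% rate among those retained becomes 0.30 × 0.80 = 24% at 20% dropout and 0.30 × 0.60 = 18% at 40%. Dropout lowers this endpoint.

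**4. Where ET tests matter.** Table 3, Section 12.3 and Appendix A schedule no walking test at Week 4, although Section 7.1 names Week 4 among visits for safety and efficacy assessments. A subject who leaves before Week 12 therefore has no post-baseline walking value except at ET, and without it adds nothing to an MMRM on change. Week 38 is a telephone visit, so for a subject leaving in the 52 − 24 = 28 weeks after Week 24, ET is the only walking test in that interval, which is where waning would appear.

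**The case against.** The strongest reply is that the plan already contains the remedy. The MMRM covers Weeks 12, 24 and 52 with a sequence-by-visit interaction, is run on the MITT set, and in the first simulation recovers the true value. The responder analysis counts those who leave, Section 14.9 tabulates withdrawals by sequence, and nothing in the protocol calls the descriptive means the main result. Much of this stands. What remains is that both descriptions of the model's contrasts are between sequences and no within-sequence LS mean is promised, while the responder endpoint does not cover continuous T25FW, TUG, 2MWT or MSWS-12.

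A reader might also infer three stronger things that the documents do not support:

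- **That ET tests enter no analysis.** Sections 14.3 and 14.5 leave details to the SAP, so the protocol's silence shows only that their use is undefined. Table 3's pairing of Week 52 with ET may be only a scheduling label; Tables 4 and 5 use it for weight and laboratory tests.
- **That everyone who stops drug is withdrawn.** Section 8.5 says so, but Section 8.3 words it conditionally.
- **That dropout will be driven by response.** The reasons in Section 8.5 for stopping drug do not include lack of efficacy. The list is not exhaustive, and Section 8.3 allows consent to be withdrawn, so the possibility stays open but unproven.

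Finally, efficacy is a secondary aim in an open-label study whose primary objective is safety. No hypothesis test or error rate rests on these means. That limits the weight of the point.

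**Conclusion.** The concern holds for the continuous measures, and it is conditional. As written, the within-sequence Week 52 summaries and the PP repeat reflect those who stayed. They overstate durability if leaving is related to response. The bias is 0.06-0.12 ft/s for 30-40% dropout and a 0.2-0.3 ft/s difference between completers and dropouts, and about zero if dropout is unrelated to response. These inputs are assumed, and the completer-minus-dropout difference at Week 52 could not be observed directly.

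It would go too far to conclude that the study's durability finding as a whole is a survivor result. The responder endpoint moves the other way, and the planned MMRM is open to this bias only where dropout depends on values not seen. The defect is that the suitable model is not assigned to the within-sequence objective, no sensitivity analysis for informative dropout is stated, and ET tests have no stated place. This should be changed, but it does not threaten the primary objective.

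**What to change.** 1. **Main continuous estimates.** Report the MMRM LS mean change with 95% CI for each sequence at Weeks 12, 24 and 52 in the MITT set, and state what it estimates for subjects who leave. Keep observed means as support, with n at each visit. Align the Synopsis and Section 14.5 on the contrasts.
2. **ET tests.** Assign ET efficacy values to the nearest scheduled visit by study day when taken on or just after drug, with an on-drug flag, and include them in the MMRM. Never count them as Week 52 by default. State the window limits, and which value counts when the visit already has a scheduled test. This will arise often: the midpoint of Weeks 24 and 52 is (24 + 52) / 2 = 38, so an exit between Weeks 24 and 38 falls nearest to Week 24.
3. **Sensitivity analysis.** Add a delta-adjusted missing-not-at-random analysis that makes the values of withdrawn subjects worse by a range of amounts fixed in advance. Setting them to no change from baseline would be lenient for sequences 2 and 3: Week 0 is the Week 16 visit of Study MS301, after active treatment, so no change would credit them with retained benefit. Limit the no-imputation sentence to the descriptive summaries.
4. **Withdrawal wording.** Sections 8.3 and 8.5 on withdrawal after stopping study drug must be reconciled.

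The cost is SAP wording, a short protocol clarification and a few extra tables from data already collected. The downside is that some ET values are taken shortly after the last dose, hence the on-drug flag.

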#### Efficacy Analyses

All efficacy analyses will be based on the MITT, as well as the PP analyses set.

Endpoints will be summarized by treatment sequence depending on the treatment received in Study ADS-AMT-MS301:

Sequence No.	Study ADS-AMT-MS301 Treatment	Study ADS-AMT-MS303 Treatment
1	Placebo	274 mg/d ADS-5102
2	137 mg/d ADS-5102	274 mg/d ADS-5102
3	274 mg/d ADS-5102	274 mg/d ADS-5102

Efficacy results will be analyzed by treatment sequences 1, 2, and 3 shown above and also by sequences 2 and 3 combined (ie, treatment sequence 1 versus 2 and 3 combined). Descriptive statistics (ie, mean, standard error, median, minimum/maximum, 95% confidence intervals [CI] for the changes from baseline) for each parameter at each study visit will be generated. Missing data will not be imputed. Graphical depictions of changes over time will be provided.

The proportion of Novel Responders in walking speed for each treatment sequence as well as pooled sequences 2 and 3 will also be characterized. The counts and percentages of Novel Responders, Non-Responders and discontinuations at each study visit will be presented.

For parameters measured on a continuum (eg, MSWS-12, T25FW (ft/sec)), the treatment-sequence time trend will be explored using a Mixed Model Repeated Measures (MMRM) model with the change from baseline as the dependent variable, fixed effects of treatment-sequence, study visit (ie week 12, 24 and 52), treatment-sequence by study visit interaction, baseline value as a covariate and an unstructured variance-covariance matrix for the within-subject residual variability. Appropriate contrasts comparing specific weeks between treatment-sequences will be derived from this model. For the proportion responders, a GEE (generalized estimating equation) model for a binomial variate will be used.

Details of all analyses will be provided in the statistical analysis plan (SAP) for this study.

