## 12. EVALUATIONS BY VISIT

A schedule of study evaluations is provided in [Appendix A](#).

All study visits should occur on the day scheduled  $\pm$  2 days.

### 12.1. Baseline/Week 0

Potential subjects for the study will be fully informed about the nature of the study and possible AEs. Subjects who wish to participate in the study must read and understand the consent form and sign the document after the investigator has answered all questions to the candidate's satisfaction. Further procedures can begin only after the consent form has been signed.

The Week 16 Visit of Study ADS-AMT-MS301 will serve as the Baseline/Week 0 study visit of Study ADS-AMT-MS303 for those subjects who consent to participate. Per the Schedule of Events in [Appendix A](#), procedures that are shared between Study ADS-AMT-MS301 (Week 16 Visit) and the Baseline/Week 0 visit of the present study do not need to be repeated and the data will be captured in both studies.

The following procedures will be performed to establish each subject's qualifications for enrollment into the study:

- The subject is fully informed about the study and gives written informed consent to participate in the study
- Review inclusion/exclusion criteria and evaluate initial subject eligibility
- Record demographic information
- Medical history with an emphasis on the subject's MS and walking impairment, and past treatments for these conditions; alcohol and drug use, other neurological diseases, psychiatric disorders including Major Depressive Disorder or symptom (eg, hallucinations, agitation, paranoia, suicidal ideation), history of seizures, stroke or transient ischemic attack (TIA); history of myocardial infarction (MI) or congestive heart failure (CHF); and history of cancer
- Record all medications currently taken
- Assess and record AEs
- Complete physical examination
- Obtain subject weight in kilograms
- Vital signs (blood pressure, respiratory rate, heart rate, and temperature)
- Blood sample for central laboratory analysis including hematology, serum chemistry, and eGFR
- Urinalysis

- Blood sample for serum pregnancy test in female subjects of childbearing potential
- MSWS-12, T25FW, TUG, and 2MWT assessments (Full details on how individual efficacy assessments are to be performed will be provided in the study manual. These assessments are to be done in this order.)
- Administer the C-SSRS (administration instructions and forms will be provided in the study manual)

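### The MMRM adjusts for an on-treatment Week 0 value, so its specific-week sequence contrasts shrink if MS301 treatment shifted Week 0

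*Combined protocol and SAP*

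**What the plan says.** Section 14.4 fixes the efficacy baseline: "Endpoints will be derived using the Week 0 assessments as the baseline value". Section 12.1 says where that value comes from: "The Week 16 Visit of Study ADS-AMT-MS301 will serve as the Baseline/Week 0 study visit of Study ADS-AMT-MS303". Section 7.1 admits subjects "who completed study drug treatment for 16 weeks and completed a Week 16 visit in Study ADS-AMT-MS301", and no washout between the studies is described.

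The sequences being compared are the MS301 arms (placebo, 137 mg/d, 274 mg/d), all followed by 274 mg/d in MS303. Section 14.2 says of the MITT set: "It is understood that randomization here refers to the randomized assignment in study ADS-AMT-MS301".

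For continuous measures, the Section 14.5 model for change from baseline has sequence, visit (Weeks 12, 24 and 52) and their interaction, with "baseline value as a covariate and an unstructured variance-covariance matrix for the within-subject residual variability". No baseline-by-visit term is listed. The Synopsis gives the same model, but the two places differ on what is taken from it:

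- Section 14.5: "Appropriate contrasts comparing time trends between treatment-sequences will be derived from this model".
- Synopsis, Efficacy Analyses: "Appropriate contrasts comparing specific weeks between treatment-sequences will be derived from this model".

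Section 14.5 also plans descriptive statistics by sequence and visit, including "95% confidence intervals [CI] for the changes from baseline". It presents the MMRM as exploratory and leaves details to the SAP.

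**The concern.** Adjusting for a pre-randomisation baseline is routine and harmless. Here the covariate is measured after MS301 randomisation, while subjects are on the treatment that defines the sequence. Section 5.4 gives a reason to expect it to differ by arm: a significant Phase 2 effect of 274 mg on walking speed and an anticipated dose-response.

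If it does differ, comparing sequences at a common Week 0 value matches placebo subjects who reach that speed unaided with drug subjects who reach it with help (Lord's paradox). When rho is below 1, the slope of change on Week 0 is negative. The adjustment then takes gain away from sequence 1 and credits it to sequence 3.

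Section 5 gives the study two efficacy aims: supportive evidence from treating former placebo subjects, and durability up to 64 weeks. The shift would understate the first and could blur the second. Contrasts at a given week matter because the first modelled visit is Week 12. Catch-up completed by then shows only in levels, not in differences between later visits.

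**Working it through.** The documents state no effect size, SD, correlation or allocation ratio for this analysis, so there is no planned figure to reproduce. The check is algebra, backed by simulation.

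**Inputs from the documents.** The covariate and its timing (Sections 12.1, 14.4), the definition of the sequences (14.2, 14.5), one baseline slope (14.5), and up to about 540 subjects (14.1).

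**Assumptions.** d is the MS301 effect of 274 mg at Week 0. The 137 mg effect is half of d. All sequences are at the same level after Week 0 (full catch-up). There are 180 subjects per sequence. rho is the within-sequence slope of the later value on the Week 0 value.

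**Formula.** The slope of change on Week 0 is b = rho - 1. For sequences 1 and 3, whose Week 0 means differ by -d:

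adjusted contrast = unadjusted contrast - b x (-d) = unadjusted contrast - (1 - rho) x d

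A sequence's LS mean at the overall Week 0 mean is its mean change minus b x (its Week 0 mean - overall Week 0 mean). The Week 0 means are 0, 0.5d and d, so the overall mean is 0.5d. At rho = 0.8:

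- Sequence 1: 1.00d - (-0.2)(-0.5d) = 0.90d
- Sequence 3: 0 - (-0.2)(0.5d) = 0.10d

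| Model | Seq 1 | Seq 3 | Seq 1 - 3 | Seq 1 - (2 and 3) |
|---|---|---|---|---|
| No Week 0 covariate | 1.00d | 0 | 1.00d | 0.75d |
| Covariate, rho 0.7 | 0.85d | 0.15d | 0.70d | 0.525d |
| Covariate, rho 0.8 | 0.90d | 0.10d | 0.80d | 0.60d |
| Covariate, rho 0.9 | 0.95d | 0.05d | 0.90d | 0.675d |

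With d = 0 every shift is zero. With rho above 1 the direction reverses (rho = 1.1 gives 1.10d). For tests where lower is better, the direction in terms of benefit is the same.

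**Time trends.** With one slope, the shift is the same at every visit, so it cancels from a contrast such as Week 52 minus Week 12.

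**Simulated MMRM** (unstructured covariance, d = 0.3 SD):

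- At rho = 0.8 without dropout, the sequence 1 minus 3 contrasts at Weeks 12/24/52 were 0.79d/0.79d/0.79d with the covariate and 0.99d/1.00d/1.00d without it. The Week 52 minus Week 12 contrast was 0.007d in both.
- With 25% dropout (unrelated to outcome), or with rho declining over visits, the two trend contrasts still agreed within 0.002d.
- With a baseline-by-visit term added and rho declining 0.85/0.80/0.70, the trend contrast moved by about -0.15d.

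**Size relative to noise.** At d = 0.3 SD, shift/SE = (1 - rho) x 0.3 / [sqrt(2/180) x sqrt(1 - rho²)]. This is 0.06/(0.1054 x 0.600) = 0.95 at rho 0.8, and 0.03/(0.1054 x 0.436) = 0.65 at rho 0.9.

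**Cost in precision.** Without the covariate, SE = SD x sqrt(2(1 - rho)) x sqrt(2/180). With an assumed SD of 0.7 ft/s this is 0.0572, 0.0467 and 0.0330 at rho 0.7, 0.8 and 0.9. Simulated SEs with the covariate at a single visit were 0.0531, 0.0446 and 0.0324. The ratios are 1.08, 1.05 and 1.02.

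**The case against.** A reader might infer that every sequence contrast in Section 14.5 is biased. The documents do not support that. That section names time-trend contrasts, and with a single slope these are untouched. This part of the objection stands in full; the exposure is in the Synopsis wording.

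A reader might also take the bias as established. It is not. MS301 was still running when the protocol was written, and neither d nor rho is given.

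Third, an unaffected figure is already planned: the descriptive changes with 95% intervals show the sequence 1 gain without adjustment. That stands too. However, those intervals are listed for changes from baseline, and the MMRM is the source named for between-sequence contrasts of the continuous measures.

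Fourth, it is tempting to say the adjustment hides waning in sequence 3. Waning from Week 12 to Week 52 is a time trend and is unaffected. The spurious LS mean gain also needs evaluation at the overall Week 0 mean, which the plan does not specify. With d = 0.20 ft/s and SD 0.7 ft/s (both assumed), simulated gains of 0.030, 0.020 and 0.009 ft/s at rho 0.7, 0.8 and 0.9 are about 0.8, 0.6 and 0.4 of a single-sequence SE (contrast SE divided by sqrt 2).

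Finally, the sequences contain only MS301 completers who consented, so they are no longer intact randomised groups. It would be too strong to call these contrasts the study's only internally controlled efficacy evidence. No choice of covariate repairs that selection. None of this removes the shift from the specific-week contrasts.

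**Conclusion.** The concern holds conditionally and for part of the output. The specific-week contrasts in the Synopsis, any time-averaged sequence contrast, and any LS mean taken at the overall Week 0 mean depend on a covariate that MS301 treatment may have moved. If it did so by d, and rho is below 1, the sequence 1 minus 3 contrast loses (1 - rho) x d: 20% of a full catch-up at rho 0.8 and 10% at rho 0.9. The sequence 3 LS mean change gains about 0.10d or 0.05d, taking the 137 mg effect as half of d.

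Between-visit trend contrasts are safe only while the baseline slope is common to all visits. The analysis is exploratory and efficacy is a secondary objective, so the primary safety objective is not touched. The correction is still worth making, because the two descriptions of the contrasts disagree and only one of them is robust to this problem.

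**What to change.** 1. Reconcile Section 14.5 with the Synopsis on which sequence contrasts come from the MMRM.
2. For specific-week or time-averaged sequence contrasts, omit the Week 0 covariate. Alternatively, replace it with the MS301 pre-randomisation value of the same test, if that was collected and can be linked. Section 14.6 already refers EDSS change to MS301 Screening, but this does not show that the walking measures are available. Omission alone removes the shift.
3. Report within-sequence LS means at each sequence's own Week 0 mean.
4. If Week 0 stays in the model for trend contrasts, state that its slope is common to all visits.

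The cost is SAP wording, a contrast SE about 2% to 8% larger (rho 0.9 to 0.7), and a data merge if the MS301 value is used. No visit or assessment changes. A further cost is that, without Week 0, the model no longer conditions on Week 0 performance when dropout depends on it; the simulation did not test that kind of dropout.
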